9 STATISTICAL PLAN

Continuous variables will be expressed as mean (or median) and range or standard deviations. Categorical variables will be expressed as frequencies. The diagnostic efficacy of [⁶⁸Ga]Galmydar and ¹³N-ammonia PET MPI will be assessed following blinded and independent reads of PET MPI data using ICA as the truth standard. Analysis of diagnostic efficacy will be performed by the reader. The analysis of diagnostic certainty will be a modified majority rule in which the median rating will be used when three readers have 3 different ratings. Similarly, summaries and comparisons of Summed Stress Score (SSS), the Summed Rest Score (SRS), and the Summed Difference Score (SDS) measures will use the median of the results of 3 blinded readers. The sensitivity and specificity and corresponding 95% confidence interval of each radiotracer will be reported. Normalcy rate will be determined in the patients with a low likelihood of CAD and no ICA and be calculated as % of patients with normal/probably normal studies. Agreement for the diagnostic efficacy (presence/absence of CAD) between [⁶⁸Ga]Galmydar and ¹³N-ammonia PET MPI will be compared using a kappa statistic. The agreement between the quality of scan will be assessed using a weighted kappa and the SUV uptake will be assessed using an intra-class correlation coefficient. The ROC analysis will be performed using 17 segment model (according to the American Heart Association Guidelines) to assess the diagnostic efficacy in detection of obstructive coronary disease. The area under ROC and confidence intervals will use the empirical approach developed by DeLong, et al.⁶⁸ The inter-reader agreement between 3 blinded readers will be estimated by comparison of dichotomized ratings (normal/abnormal) and presented using kappa and percent agreement. Intra-reader agreement in each of the reader will be performed by randomizing 10% of the repeat images in the blinded read and will be estimated using kappa and percent agreement. All tests will be two-sided and a significance level of 5%.

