4.1 Study Population

We will recruit up to 38 participants for the dosimetry and rest/stress groups. Healthy adult normal volunteers (n=8, 4 males; 4 females) for whole-body imaging (dosimetry group) and patients who had a prior clinical SPECT MPI examination that is positive or negative for ischemia.

Thirty (30) subjects will be enrolled in the rest/stress group. Symptomatic patients (n=20) will have undergone a SPECT MPI examination. Ten patients in this group will have had a study positive for ischemia in two myocardial segments and referred for invasive coronary angiography (ICA) as part of their routine standard-of-care. [⁶⁸Ga]Galmydar PET imaging will occur prior to intervention. The other ten patients will have a normal SPECT MPI and no ICA referral. Subjects (n=10) who are asymptomatic and without history of cardiovascular disease will serve as a normal controls.

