4.4.2 Rest/Stress Group

For the rest/stress group, we will recruit 30 subjects. The first set will be symptomatic patients (n=20) who have undergone a SPECT MPI examination. Half of these patients will have had a study positive for ischemia in two myocardial segments and referred for invasive coronary angiography (ICA) as part of their routine standard-of-care (n=10). Subjects will undergo [⁶⁸Ga]Galmydar PET/CT prior to any intervention. The second half of these patients will have had a normal SPECT MPI and no ICA referral (n=10). A second set of subjects who are normal, asymptomatic, and without a history of cardiovascular disease will serve as controls (n=10).

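### The DeLong interval fixed for the AUC is unsuited to ten ICA patients: at patient level it can collapse to zero width or be non-computable, and the ROC unit is not stated

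*Combined protocol and SAP*

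**What the plan says.** Section 9 assesses the diagnostic efficacy of both tracers "using ICA as the truth standard". For the ROC analysis it states "The area under ROC and confidence intervals will use the empirical approach developed by DeLong". No alternative is named for small or degenerate samples. The sentence just before ties the ROC analysis to the 17-segment model but does not say whether the unit is the patient, the vessel or the segment.

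Who has the truth standard follows from section 4.1: "Ten patients in this group will have had a study positive for ischemia in two myocardial segments and referred for invasive coronary angiography (ICA"). Section 4.4.2 gives the same number. For the rest of the rest/stress group, section 4.1 says "The other ten patients will have a normal SPECT MPI and no ICA referral" and "Subjects (n=10) who are asymptomatic and without history of cardiovascular disease will serve as a normal controls". Section 9 has a separate use for patients without angiography: "Normalcy rate will be determined in the patients with a low likelihood of CAD and no ICA".

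Section 8.1.3 defines significant CAD per patient, by one or more coronary stenoses at the 50% threshold. It gives no rule for assigning a stenosis to segments. Section 4.6 replaces participants who do not complete the procedures, so ten is the planned number with ICA. Section 9.1 gives a precision figure for kappa only.

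**The concern.** DeLong's interval is a large-sample Wald interval. Its standard error is built from sample variances within the CAD-positive and the CAD-negative patients. At most ten patients have ICA, and all are selected on a positive SPECT and a referral, so one of the two groups may hold only a handful of patients. In that setting the variance estimate can be zero or undefined, and the plan gives no alternative.

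What is at stake is the stated uncertainty of the AUC for each tracer. A report of 1.00 with limits 1.00 to 1.00 from ten patients would claim certainty that the data cannot supply. It is most likely when the tracer performs well, which is the result the study hopes for.

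**Working it through.** **1. The plan's own precision figure.** Section 9.1 uses N = 20, kappa 0.8 and SD 0.3. The limits are 0.8 ± 1.96 × 0.3/√20 = 0.8 ± 0.131, that is 0.669 to 0.931, width 0.26. This reproduces. It concerns agreement between tracers in 20 patients and says nothing about the AUC.

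**2. DeLong's variance.** Let m be the number of CAD-positive and n the number of CAD-negative ICA patients, with m + n = 10. V10 is, for each positive patient, the share of negatives scored lower (ties count one half). V01 is, for each negative patient, the share of positives scored higher. The variance is var(V10)/m + var(V01)/n and the limits are AUC ± 1.96 SE.

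- Perfect separation: every V10 and V01 equals 1, both sample variances are 0, and the interval is 1 to 1.
- n = 1: var(V01) divides by n − 1 = 0 and cannot be computed.
- n = 0: the AUC is undefined.

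**3. Chance of 0 or 1 CAD-negative patients.** If a share q of ICA patients is CAD-negative (assumed), the probability is (1 − q)^10 + 10q(1 − q)^9:

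- q = 0.10: 0.349 + 0.387 = 74%
- q = 0.20: 0.107 + 0.268 = 38%
- q = 0.30: 0.028 + 0.121 = 15%
- q = 0.40: 0.006 + 0.040 = 5%

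**4. Patient-level coverage.** The model is binormal with continuous scores and at least 20,000 simulated trials per setting. Splits and true AUC are assumptions.

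| Positive/negative | Coverage at AUC 0.75 / 0.85 / 0.90 / 0.95 | Zero width at the same AUCs |
|---|---|---|
| 8/2 | 70 / 67 / 56 / 36% | 16 / 31 / 44 / 64% |
| 7/3 | 82 / 76 / 65 / 43% | 10 / 23 / 35 / 57% |
| 6/4 | 86 / 81 / 68 / 47% | 7 / 19 / 32 / 53% |
| 5/5 | 87 / 81 / 70 / 48% | 30% at 0.90, 52% at 0.95 |

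With scores cut to four categories, as in the readers' overall rating (section 8.1.2), true AUCs become 0.78 to 0.93. For 2 to 5 negatives, coverage is 50 to 83% and zero width occurs in 5 to 49% of trials.

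**5. Where the loss comes from.** Over the 8/2, 7/3 and 6/4 splits, intervals that do not collapse cover 98 to 99.9% at AUC 0.85 to 0.95 and 84 to 93% at 0.75. Their median width, truncated to the 0–1 range, is 0.28 to 0.62. Most of the loss is the collapse itself.

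**6. Other readings of the ROC analysis.**

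- Segments as the unit (10 × 17 = 170, with 30% diseased assumed): no zero-width intervals. Coverage is 93 to 94% if segments were independent, and 71 to 88% under two assumed levels of intra-patient correlation.
- Subjects without ICA counted as negative (splits 7/13, 7/23, 8/22): coverage 69 to 89%, zero width in 0 to 21%.

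**7. An interval that does not collapse.** Newcombe's Wilson-type interval solves |AUC − θ| = 1.96 √v(θ), where v(θ) = {θ(1 − θ) + (N* − 1)[θ/(2 − θ) − θ²] + (N* − 1)[2θ²/(1 + θ) − θ²]}/(mn) and N* = (m + n)/2. For 8/2 with observed AUC 1, try θ = 0.532. Then v = [0.2490 + 4(0.3624 − 0.2830) + 4(0.3695 − 0.2830)]/16 = 0.0570, and 1.96 × √0.0570 = 0.468 = 1 − 0.532. The lower limit is therefore 0.53. For 7/3 and 6/4 it is 0.60 and 0.63. Coverage in the settings of step 4 is about 94 to 97%.

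**The case against.** The strongest objection is about the unit. The sentence next to the DeLong rule names the 17-segment model, and section 8.1.2 scores every segment, so a segment-level ROC is a natural reading. On that reading the small number of CAD-negative patients does not break the interval. This stands as far as the collapse goes. It does not rescue the method, because plain DeLong then treats correlated segments as independent. Section 8.1.3 also gives only a per-patient CAD rule, and the segment scores feed per-patient summed scores, so the patient level is the better supported reading.

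A reader might infer that the limits will certainly come out far too narrow. The documents do not support that. Collapse is a matter of chance, and intervals that escape it are usually wide. A reader might also take it as given that very few ICA patients will be CAD-negative. That is a fair inference from how they are selected, but no document gives a share or an expected AUC. The worst figures, 36% coverage and 64% zero width, need both an 8/2 split and an AUC of 0.95. The conclusion itself survives an even split.

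It is also fair to say that this is a phase 0/1 feasibility study. No success criterion rests on the AUC, the primary objective stresses blood-flow comparison, and with ten verified patients any honest interval will be wide. That lowers the severity but does not make a 1-to-1 interval acceptable.

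Finally, one might extend the criticism to sensitivity and specificity. Section 9 says only "The sensitivity and specificity and corresponding 95% confidence interval of each radiotracer will be reported" and names no method, so no stated rule is wrong there.

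**Conclusion.** The point holds and should be fixed: the AUC interval rule is wrong as written. At patient level, with 2 to 5 of ten ICA patients CAD-negative and a true AUC of 0.75 to 0.95, the nominal 95% interval covers about 36 to 87%. It has zero width in about 7 to 64% of trials. The chance that it cannot be formed at all is 5 to 74% as the CAD-negative share falls from 40 to 10%. The shares, the AUCs and the binormal model are assumptions. The two algebraic failures, at perfect separation and with a single CAD-negative patient, are not. At segment level the defect changes to ignored clustering, with coverage of 71 to 88% under the assumed correlations. The plan does not say which reading applies, and that is part of what needs correcting. Nothing here shows that the study's conclusions hinge on this interval.

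**What to change.** Amend the ROC sentences in section 9 to state three things:

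- The ROC analysis uses one score per patient derived from the 17-segment scores, for example the summed stress score, in the patients with ICA.
- The 95% interval for the AUC is one that does not collapse at an AUC of 1, such as the Wilson-type Newcombe interval, in place of DeLong.
- The AUC is reported as not estimable if no ICA patient is CAD-negative.

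If a segment- or vessel-level ROC is intended, say so, give the rule that links stenoses to segments or vessels, and use an interval that clusters on the patient. The Newcombe interval would not cure that version.

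The cost is a few sentences before the reads are unblinded. The reported intervals will be wider: with perfect separation, 1.00 (1.00 to 1.00) becomes 1.00 with a lower limit of 0.53, 0.60 or 0.63 for splits of 8/2, 7/3 or 6/4. The change makes the uncertainty honest but does not make ten patients more informative.

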9.1 Sample size justification

While information in humans is not available, our preliminary animal data shows high agreement between [⁶⁸Ga]Galmydar and ¹³N-ammonia. Therefore, we expect to see strong agreement between the diagnostic efficacies of these two radiotracers in this sample of patients. A sample size of 20 patients results in a two-sided 95% confidence interval with a width of 0.26 (lower

limit=0.669, upper limit=0.931) assuming strong agreement between the radiotracers (a kappa of 0.8) and a standard deviation of 0.3. Sample size calculations were conducted in PASS v14.

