1.2.2 Rest/stress Group

A rest/stress myocardial ¹³N-ammonia PET/CT is clinically indicated for the detection of flow-limiting, obstructive coronary artery disease (CAD). Myocardial perfusion PET provides images of a higher quality than SPECT, due to higher spatial and contrast resolution, higher scanner sensitivity, and accurate attenuation correction. In addition, the concurrent quantification of myocardial blood flow (MBF) affords the assessment of hyperemic MBF during pharmacologic vasodilation and at rest and, thus, the computation of the myocardial flow reserve (MFR= MBF stress/MBF rest). The concurrent assessment of hyperemic MBF and/or MFR aids in the identification and characterization of multi-vessel CAD, microvascular dysfunction, and prognostication.

We will compare the results of [⁶⁸Ga]Galmydar PET/CT MPI to the results of ¹³N-ammonia PET/CT MPI in a group of 20 symptomatic patients and 10 normal control subjects without symptomatology. Half of the symptomatic patients recruited will have a SPECT MPI study positive for ischemia in two myocardial segments with referral for invasive coronary angiography (ICA) as part of their routine standard-of-care (n=10), and half with normal SPECT MPI and no ICA referral (n=10). Patients referred for ICA will undergo their [⁶⁸Ga]Galmydar and ¹³N-ammonia PET/CT MPI studies prior to intervention. In addition, as a completely normal control, another 10 subjects without symptomatology or known cardiovascular disease will also undergo both ¹³N-ammonia PET/CT MPI and [⁶⁸Ga]Galmydar PET/CT MPI. In total 30 patients or normal human subjects will be studied.

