8.1.2 MPI Interpretation

All images will be interpreted and blindly scored by a board certified radiologists (Drs. [name], [name], and [name]) in nuclear medicine. Both overall qualitative diagnosis and semi-quantitative 17 segment with 5 point (0=normal, 4=absent tracer uptake) scoring will be employed in the independent blind read out by 3 expert radiologists in PET MPI interpretation. To maintain consistency, the same three readers will interpret all PET studies in independent reading sessions. Importantly, these readers will be blinded to type of radiotracer, the presence or absence of stress agent, and all clinically relevant data. Image quality will also be classified as excellent, good, fair, poor, or uninterpretable. For purpose of assessing diagnostic efficacy, each blinded reader will rate the rest/stress perfusion and gated images as normal, ischemic, ischemic and scar, or scar. A

patient will be defined as MPI negative if the rating will be normal. Summed stress scores (SSS), summed rest scores (SRS), and summed difference scores (SDS) will also be calculated ⁶⁴. Absolute regional myocardial blood flow will also be reported.

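### Section 9.1's interval for kappa (0.669 to 0.931, n=20) rests on an SD of 0.3 that a present/absent kappa of 0.8 cannot have; the expected interval is about twice as wide

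*Combined protocol and SAP*

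**What the plan says.** Section 9.1 supports the sample size with one calculation: "A sample size of 20 patients results in a two-sided 95% confidence interval with a width of 0.26". The limits and inputs follow: "limit=0.669, upper limit=0.931) assuming strong agreement between the radiotracers (a kappa of 0.8) and a standard deviation of 0.3". It names PASS v14 as the software, but gives no source for the SD and no expected proportion of positive calls.

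Section 9 defines the rating: "Agreement for the diagnostic efficacy (presence/absence of CAD) between [⁶⁸Ga]Galmydar and ¹³N-ammonia PET MPI will be compared using a kappa statistic". Section 8.1.2 gives the rule that makes each read binary: a "patient will be defined as MPI negative if the rating will be normal". No interval method for kappa is named, although one is named for the ROC area.

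On the mix of patients, Section 1.2.2 says "Half of the symptomatic patients recruited will have a SPECT MPI study positive for ischemia in two myocardial segments" and "half with normal SPECT MPI and no ICA referral (n=10". That is 10 and 10 among the 20 symptomatic patients.

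**The concern.** For a continuous measurement, the SD is a separate planning input. For a kappa on a two-category rating it is not: once kappa and the two positive rates are set, the large-sample SD follows. Section 9.1 sets kappa at 0.8 and then adds an SD of 0.3 as if it were free. If the two values cannot occur together, the stated interval describes no possible version of this study.

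At stake is the only quantitative argument for 20 patients. A reader of Section 9.1 would expect that, if agreement really is 0.8, the study will place it above roughly 0.67. If the SD is too small, the study will say much less than that about whether the new tracer agrees with ¹³N-ammonia.

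**Working it through.** **Inputs.** From Section 9.1: n = 20, 95% two-sided (z = 1.96), kappa κ = 0.8, SD = 0.3, limits 0.669 and 0.931. From Section 9: a binary rating. The positive rate p of the PET calls is not stated. I assume 50%, from the 10/10 SPECT split, and show a range.

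**1. The plan's figure.** κ ± z·SD/√n = 0.8 ± 1.96 × 0.3/√20 = 0.8 ± 0.1315, or 0.6685 to 0.9315, width 0.263. This matches, so 0.3 is a per-patient SD.

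**2. The SD that goes with κ = 0.8.** With equal positive rates p for both tracers, chance agreement is pe = p² + (1 − p)² and observed agreement is po = pe + κ(1 − pe). The simple large-sample SD is √[po(1 − po)]/(1 − pe). At p = 0.5: pe = 0.50, po = 0.90, SD = √(0.9 × 0.1)/0.5 = 0.3/0.5 = 0.60. The full Fleiss-Cohen-Everitt variance also gives 0.600. Other rates, with the full variance and n = 20:

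| Positive rate | SD | 0.8 ± 1.96·SD/√20 | Width | Width cut at 1 | Width / 0.263 (uncut) |
|---|---|---|---|---|---|
| 50% | 0.600 | 0.537 to 1.063 | 0.526 | 0.463 | 2.0 |
| 40% | 0.613 | 0.531 to 1.069 | 0.537 | 0.469 | 2.0 |
| 30% | 0.658 | 0.512 to 1.088 | 0.577 | 0.488 | 2.2 |
| 20% | 0.759 | 0.467 to 1.133 | 0.665 | 0.533 | 2.5 |

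**3. Can any table give 0.3?** A search over all 2×2 tables with kappa 0.8, including unequal positive rates, gives a minimum SD of about 0.585. An SD of 0.3 needs a kappa of 0.954 (50% positive) to 0.971 (20% positive), above the plan's own upper limit of 0.931.

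**4. A possible origin.** The 0.3 equals √(0.9 × 0.1), the SD of raw agreement at 50/50 before division by 1 − pe = 0.5. The documents do not say this is where it came from.

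**5. An interval that respects the upper bound of 1.** The goodness-of-fit (Donner-Eliasziw) interval takes the κ values at which the chi-square distance from the expected table equals 3.84. At 50% positive the expected table of 20 is 9/1/1/9 (two discordant patients), and the condition reduces to 20(κ − 0.8)²/(1 − κ²) = 3.84. Its solutions are κ = 0.398 and 0.944, a width of 0.546, or 2.1 times the stated one. At 40% positive the interval is 0.39 to 0.95, at 30% it is 0.36 to 0.95, and at 20% it is 0.31 to 0.96.

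**6. What the estimate will do.** If κ = 0.8 and 50% are positive, the estimate falls inside 0.669 to 0.931 about 72% of the time, below it 16% and above it 12%. The 12% is simply the chance of no discordant patient, 0.9²⁰ = 0.12. With balanced margins, two discordant patients give kappa 0.8 and four give (0.80 − 0.50)/0.50 = 0.6, already below the stated lower limit.

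**7. Coverage at n = 20.** At 50% positive, the goodness-of-fit interval covers about 95.5% and the Wald interval cut at 1 about 86.5%.

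**8. Sample size for the stated width.** At SD 0.60, n = (2 × 1.96 × 0.60/0.263)² ≈ 80.

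**The case against.** The arithmetic in Section 9.1 is correct, and the SD is openly presented as an assumption. That stands: the fault is an unattainable input, not a miscalculation.

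Twice as wide describes an interval that runs past 1. Cut at 1, the plan's own method is 1.8 times as wide at 50% positive; a ratio of about two needs either the uncut interval or a different method. This also stands, and the lower limit (0.54 instead of 0.669) is the safer single number. The ratio depends on an assumed positive rate, but uneven splits only make it larger.

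Other readings of the plan do not rescue 0.3:

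- **Four-category rating.** Section 8.1.2 has four categories, but Section 9 specifies presence or absence. With four equally frequent categories the SD would be √(0.85 × 0.15)/0.75 = 0.476.
- **All 30 rest/stress subjects.** Section 9.1 says 20. With 30 at SD 0.60 the width is 0.43. Section 9 does not say who enters the kappa, so taking the 20 symptomatic patients is a natural reading that should be written down.
- **Three readers.** Section 9.1 counts patients. Three fully independent readings would give at best 0.60/√3 = 0.35.

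The goodness-of-fit method is partly a preference, and it assumes a common positive rate for both tracers. The team may choose another method if it states its behaviour at n = 20.

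Finally, this is a small phase 0/1 study, with no kappa threshold or stopping rule, and the reported interval will come from the trial data. That limits the consequence; it does not make the planning statement right.

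**Conclusion.** The concern holds. No present/absent kappa of 0.8 has a large-sample SD of 0.3: the smallest possible is about 0.585, whatever the positive rates. This needs no assumption beyond the binary rating set in Section 9.

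The size of the error rests on 20 patients and an assumed 50% positive calls. The expected lower limit is then 0.54 by the plan's formula, or 0.40 by a method that holds its coverage at this sample size, against 0.669 stated. The width is 1.8 to 2.1 times the stated one, depending on method. The large-sample SD is approximate at n = 20, but simulation supports it: the SD of the estimate is about 0.14, against 0.3/√20 = 0.067 implied by the plan.

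This is a wrong precision statement that should be corrected. It does not invalidate a decision rule, because the plan has none for kappa.

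**What to change.** Keep n = 20. Remove the SD of 0.3 and the interval 0.669 to 0.931, and restate Section 9.1 along these lines:

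> With the 20 symptomatic patients, an assumed 50% positive calls on each tracer and a kappa of 0.8 (expected table 9/1/1/9), the expected two-sided 95% goodness-of-fit confidence interval for kappa is about 0.40 to 0.94 (0.39 to 0.95 at 40% positive, 0.36 to 0.95 at 30%).

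In Section 9, name the same interval method for the tracer-agreement kappa and say that the 20 symptomatic patients enter it, if that is the intent. If the team prefers Wald, quote 0.54 to 1.00 (SD 0.60, cut at 1) and state that its coverage at n = 20 is below 95%.

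The cost is a rewording of Section 9.1 and a short addition to Section 9. The stated precision becomes less favourable. No extra patients or procedures are needed.
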